8.1. Efficacy and Immunogenicity Assessments

No generally accepted immunological correlate of protection has been demonstrated for SARS-CoV-2 to date.

8.1.1. Prespecified Criteria for Suspected COVID-19 Prior to Amendment 7

The criteria for suspected COVID-19 (ie, the triggers to proceed with home-collection of the nasal swabs on COVID-19 Day 1-2 and to proceed with the COVID-19 Day 3-5 visit) are prespecified as follows:

- **A positive RT-PCR result for SARS-CoV-2, through a private or public laboratory independent of the study, whether symptomatic or asymptomatic**

OR

- **New onset or worsening of any 1 of the symptoms listed below, which lasts for at least 24 hours, not otherwise explained:**

Headache

Malaise (appetite loss, generally unwell, fatigue, physical weakness)

Myalgia (muscle pain)

Chest congestion

Cough

Runny nose

Shortness of breath or difficulty breathing (resting or on exertion)

Sore throat

Wheezing

Eye irritation or discharge

Chills

Fever ($\geq 38.0^{\circ}\text{C}$ or $\geq 100.4^{\circ}\text{F}$)

Pulse oximetry value $\leq 95\%$, which is a decrease from baseline

Heart rate ≥ 90 beats/minute at rest, which is an increase from baseline

Gastrointestinal symptoms (diarrhea, vomiting, nausea, abdominal pain)

Neurologic symptoms (numbness, difficulty forming or understanding speech)

Red or bruised looking toes

Skin rash

- Taste loss or new/changing sense of smell
- Symptoms of blood clots: pain/cramping, swelling or redness in your legs/calves
- Confusion
- Bluish lips or face
- Clinical suspicion/judgement by investigator of symptoms suggestive for COVID-19

As several of the prespecified criteria for suspected COVID-19 overlap with vaccine-related reactogenicity, investigators' clinical judgement is required to exclude vaccine-related events when assessing suspected COVID-19.

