- If the participant has at least 1 SARS-CoV-2 positive nasal swab collected on COVID-19 Day 1-2 or Day 3-5 visits, then the participant will be asked to undertake the COVID-19 procedures (2-day cycles) until 14 days after symptom onset (COVID-19 Day 15) or until **resolution of the COVID-19 episode**, whichever comes last^a. Resolution of the COVID-19 episode is defined as having 2 consecutive SARS-CoV-2 negative nasal swabs and 2 consecutive days with no COVID-19-related signs or symptoms. Once past COVID-19 Day 15, participants should stop the collection of nasal swabs and saliva samples as soon as 2 consecutive nasal swabs are SARS-CoV-2 negative, but (if still symptomatic at that time) should continue completing the ePROs (including SIC, body temperature, and pulse oximetry) in the eCOA until 2 consecutive days with no COVID-19-related signs or symptoms.

Note: for participants who have signs and symptoms present at baseline (assessed pre-vaccination), only signs and symptoms that are associated with COVID-19 and that developed during the COVID-19 episode are to be taken into account.

- If signs and symptoms are still ongoing on **COVID-19 Day 3-5**, collection of SIC will be continued until at least 14 days after onset unless both **COVID-19 Day 1-2** and **COVID-19 Day 3-5** nasal swabs are negative. If either of the swabs is positive or the result is unknown AND the participant is beyond 14 days after onset of symptoms, the SIC can be stopped after 2 days without signs and symptoms.
- For participants with a positive test result for SARS-CoV-2 infection, a study visit will be conducted 28 days after symptom onset (ie, at the COVID-19 Day 29 visit) to assess the clinical course of the infection.
- If 2 consecutive nasal swabs negative for SARS-CoV-2 are not available due to operational reasons (eg, delays in results availability), participants may cease collection of nasal swabs and saliva samples at the COVID-19 Day 29 visit, provided they have 2 consecutive days with no COVID-19-related signs and symptoms. In these cases, participants may be asked to resume sample collection if nasal sample results once available do not present with 2 consecutive negative swabs for SARS-CoV-2

Upon closure of the COVID-19 episode and procedures, all participants will fall back to the default [Schedules of Activities](#), until the end of the study/early withdrawal.

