8.1.3.1. Case Definition for Moderate to Severe/Critical COVID-19

For the primary -endpoint (see Section 3), all moderate and severe/critical COVID-19 cases will be considered.

Case Definition for Moderate COVID-19

- A SARS-CoV-2 positive RT-PCR or molecular test result from any available respiratory tract sample (eg, nasal swab sample, sputum sample, throat swab sample, saliva sample) or other sample

AND at any time during the course of observation^a:

Any 1 of the following new or worsening signs or symptoms:

- Respiratory rate ≥ 20 breaths/minute
- Abnormal saturation of oxygen (SpO_2) but still $>93\%$ on room air at sea level*
- Clinical or radiologic evidence of pneumonia
- Radiologic evidence of deep vein thrombosis (DVT)
- Shortness of breath or difficulty breathing

Any 2 of the following new or worsening signs or symptoms:

- Fever ($\geq 38.0^{\circ}\text{C}$ or $\geq 100.4^{\circ}\text{F}$)
- Heart rate ≥ 90 beats/minute
- Shaking chills or rigors
- Sore throat
- Cough
- Malaise as evidenced by 1 or more of the following**:
 - Loss of appetite
 - Generally unwell
 - Fatigue
 - Physical weakness
- Headache
- Muscle pain (myalgia)
- Gastrointestinal symptoms (diarrhea, vomiting, nausea, abdominal pain)**
- New or changing olfactory or taste disorders
- Red or bruised looking feet or toes

OR

* SpO_2 criteria will be adjusted according to altitude, per the investigator judgement.

** Having 2 or more elements of a symptom (eg, vomiting and diarrhea or fatigue and loss of appetite) is counted only as 1 symptom for the case definition. To meet the case definition, a participant would need to have at least 2 different symptoms.

Case Definition for Severe/Critical COVID-19

^a Participants will be asked to undertake the COVID-19 procedures until 14 days after symptom onset (COVID-19 Day 15) or until **resolution of the COVID-19 episode**, whichever comes last (see Section 8.1.2).

- A SARS-CoV-2 positive RT-PCR or molecular test result from any available respiratory tract sample (eg, nasal swab sample, sputum sample, throat swab sample, saliva sample) or other sample

AND any 1 of the following at any time during the course of observation^a:

- Clinical signs at rest indicative of severe systemic illness (respiratory rate ≥ 30 breaths/minute, heart rate ≥ 125 beats/minute, oxygen saturation (SpO_2) $\leq 93\%$ on room air at sea level*, or partial pressure of oxygen/fraction of inspired oxygen ($\text{PaO}_2/\text{FiO}_2$) < 300 mmHg)

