8.1.3.2. Case Definition for Mild COVID-19

- A SARS-CoV-2 positive RT-PCR or molecular test result from any available respiratory tract sample (eg, nasal swab sample, sputum sample, throat swab sample, saliva sample) or other sample;

AND at any time during the course of observation^a:

- One of the following symptoms: fever ($\geq 38.0^\circ\text{C}$ or $\geq 100.4^\circ\text{F}$), sore throat, malaise (loss of appetite, generally unwell, fatigue, physical weakness), headache, muscle pain (myalgia), gastrointestinal symptoms, cough, chest congestion, runny nose, wheezing, skin rash, eye irritation or discharge, chills, new or changing olfactory or taste disorders, red or bruised looking feet or toes, or shaking chills or rigors.

A case is considered mild when it meets the above case definition but not the moderate to severe/critical definition in Section 8.1.3.1.

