8.1.3.4. Case Definition for Asymptomatic or Undetected COVID-19

If a participant does not fulfil the criteria for suspected COVID-19 based on signs and symptoms (see Section 8.1.1), which would classify them as mild or moderate to severe/critical by the protocol definitions mentioned above (Section 8.1.3.1 and Section 8.1.3.2).

AND

- has a SARS-CoV-2 positive RT-PCR or molecular test result from any available respiratory tract sample (eg, nasal swab sample, sputum sample, throat swab sample, saliva sample) or other sample

OR

- develops a positive serology (non-S protein) test

Then, the participant will be considered to have experienced asymptomatic or undetected COVID-19.

A molecularly confirmed positive RT-PCR for SARS-CoV-2 will need to be captured in the eCRF.

As of Amendment 7, severity assessment by the CSAC may still be performed and will be based on the data collected through the passive follow-up (eg, hospitalization reported in the context of SAEs). The scope of the severity review may change and will be described in the charter.

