9.4.2. Secondary Endpoints for the Double-blind Phase

All secondary endpoint analyses for the double-blind phase will occur in the PP analysis set, in seronegative participants unless otherwise indicated.

To evaluate the effect of the vaccine against symptomatic molecularly confirmed COVID-19, including mild infections, a BOD endpoint will be evaluated based on the first occurrence of molecularly confirmed COVID-19, including mild, moderate and severe/critical case definitions in Sections 8.1.3.1 and 8.1.3.2, with onset at least 14 days after the second vaccination (Day 71) with Ad26.COV2.S versus placebo, in the PP population, including all events across age groups, with and without comorbidities. In this study, the BOD endpoint is defined as taking the value 1 for mild and moderate disease and the value 2 for severe disease (implicitly assigning a value of 0 for no disease [not infected or asymptomatic infection]). By assigning higher weight to severe infections, the BOD endpoint aims at providing higher statistical power for differentiating from placebo vaccines with increased protection against severe infections (but potentially lower VE against milder infections). The BOD evaluates the severity-adjusted VE against preventing

symptomatic incidence. The hypothesis to evaluate the VE against symptomatic infection will be based on this method. In addition, the VE against each severity category according to the case definition (severe, moderate, mild) will be summarized separately. Statistical significance for the BOD endpoint will be tested using $H_0: VE \leq 0$ at a one-sided $\alpha = 2.5\%$ according to multiplicity adjusted strategy. Details on the calculation of VE for the BOD endpoint and its associated confidence interval (for testing) and hypothesis testing will be foreseen in the SAP.

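### The mild COVID-19 definition does not require the symptom to be new or worsening, and the asymptomatic definition takes its boundary from a different symptom rule, so the two classes can overlap

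*Protocol*

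**What the plan says.** Section 8.1.1 sets the triggers for swabbing. Its symptom route is "New onset or worsening of any 1 of the symptoms listed below, which lasts for at least 24 hours, not otherwise explained". It also has a route that needs no symptoms: "A positive RT-PCR result for SARS-CoV-2, through a private or public laboratory independent of the study, whether symptomatic or asymptomatic". A further listed item is "Clinical suspicion/judgement by investigator of symptoms suggestive for COVID-19".

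The moderate definition in 8.1.3.1 asks for one sign from a first list, or "Any 2 of the following new or worsening signs or symptoms" from a second. The mild definition in 8.1.3.2 asks for a positive molecular test and "One of the following symptoms: fever", followed by the rest of the list. Within that list only the smell and taste item says new or changing. Mild is then separated from moderate and severe/critical, but 8.1.3.2 has no sentence separating it from asymptomatic.

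Section 8.1.3.4 gives the asymptomatic or undetected class to an infected participant who "does not fulfil the criteria for suspected COVID-19 based on signs and symptoms (see Section 8.1.1"), and adds that these are the signs that would have placed the participant in the mild or worse classes.

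A note under episode closure in 8.1.2.2 says that, for participants with symptoms at baseline, "only signs and symptoms that are associated with COVID-19 and that developed during the COVID-19 episode are to be taken into account". In Section 9.4.2, "the BOD endpoint is defined as taking the value 1 for mild and moderate disease", severe disease scores 2, and asymptomatic infection scores 0.

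**The concern.** Mild and asymptomatic should be exclusive and together cover every confirmed infection below moderate. Here each is defined by its own symptom test, and 8.1.3.4 assumes that failing the 8.1.1 test is the same as not being mild. It is not, because 8.1.3.2 uses none of the three 8.1.1 conditions (new or worsening, 24 hours, unexplained).

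The boundary feeds several analyses: the burden-of-disease endpoint, which is formally tested; VE by severity category; VE against asymptomatic infection; and harm monitoring of symptomatic cases, where footnote a to Table 7 counts mild events. If a vaccine prevents asymptomatic infection less well than disease, moving asymptomatic infections into the mild class dilutes VE against symptomatic disease.

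**Working it through.** The protocol states no figure to reproduce. The check is a comparison of the definitions, followed by an illustration of size.

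**1. Conditions placed on the symptom**

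| Section | New or worsening | At least 24 hours | Unexplained |
|---|---|---|---|
| 8.1.1, symptom route | yes | yes | yes |
| 8.1.3.1, moderate | yes | no | no |
| 8.1.3.2, mild | no (smell/taste item only: new or changing) | no | no |
| 8.1.3.4, asymptomatic | by reference to 8.1.1 | by reference | by reference |

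**2. Two test cases, both with a positive molecular test**

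- *Only a chronic, unchanged cough.* This meets 8.1.3.2. It fails the symptom route of 8.1.1, so it also meets 8.1.3.4 if the reference to 8.1.1 governs. If the closure note in 8.1.2.2 were applied to classification, the cough would drop out and only asymptomatic would remain; but the note sits among the rules for stopping procedures.
- *Only a new headache lasting under 24 hours.* This gives the same overlap, and the closure note does not help.

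Section 8.1.3 bases severity on the most severe grade reached and cites 8.1.3.1, 8.1.3.2 and 8.1.3.4. That points both cases towards mild, a burden-of-disease score of 1 rather than 0.

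**3. Where such cases can arise**

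Mild needs a molecular test, so infections found by serology alone cannot be affected. Most study swabs follow 8.1.1 symptoms. The exposed group is mainly:
- participants with an external positive test, who are swabbed under 8.1.2.2 whether or not they have symptoms;
- participants positive on a scheduled swab, such as the one taken from everyone at the unblinding visit (8.8);
- participants assessed on COVID-19 Day 1, before 24 hours have passed, or whose symptoms had gone by Day 3-5 and who were recalled on a positive swab.

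The symptom questionnaire (SIC, Appendix 6) asks only about the last 24 hours and does not ask whether a symptom is new.

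**4. Illustration under assumed inputs**

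Let r be the ratio of PCR-detected asymptomatic to symptomatic infections on placebo, and q the share of the former relabelled as mild. Assume VE of 65% against symptomatic disease (the value 9.2.1 uses for moderate to severe/critical disease) and 20% against asymptomatic infection. Then

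observed VE = 1 − [0.35 + 0.80·r·q] / (1 + r·q)

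- r = 0.3, q = 0.1: 1 − 0.374/1.03 = 63.7%
- r = 0.3, q = 0.4: 1 − 0.446/1.12 = 60.2%
- r = 0.5, q = 0.1: 1 − 0.390/1.05 = 62.9%
- r = 0.5, q = 0.4: 1 − 0.510/1.20 = 57.5%

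The protocol gives neither r, nor q, nor the 20%. These results show direction and scale only. They allow nothing for adjudication or for the surveillance filters below.

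**The case against.** The strongest reply is that 8.1.3.4 can be read as already separating the classes. Its clause about signs that would place a participant in the mild or worse classes cites 8.1.3.1 and 8.1.3.2, so anyone meeting mild would not be asymptomatic. That reading is open. It removes the double classification but leaves the missing condition in 8.1.3.2: the participant with only a chronic cough is then simply mild.

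Second, chronic symptoms are partly filtered earlier. Routine surveillance asks about new symptoms, the questionnaire after an external positive is completed only if COVID-like symptoms are present, and the closure note shows the intent to ignore baseline symptoms. Third, 8.1.3.6 makes the adjudication committee's classification definitive, and 8.1.3 allows it clinical judgement. The SAP or the charter may add a derivation rule; neither was available here. These points stand as limits on how many cases are affected, but they do not supply the missing condition.

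Fourth, swab triggers, closure rules and endpoint definitions need not be identical. That is fair, but 8.1.3.4 itself turns a trigger into an endpoint boundary.

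A reader might also infer that suspected COVID-19 always requires a 24-hour symptom. It does not: an external positive RT-PCR is enough, and investigator judgement is listed. What matters is that 8.1.3.4 refers only to the signs-and-symptoms criteria, so the external-test route does not take a participant out of the asymptomatic class.

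**Conclusion.** The inconsistency is real and confined to secondary endpoints and harm monitoring. As written, 8.1.3.2 admits unchanged chronic symptoms that 8.1.3.1 excludes, and 8.1.3.4 wrongly treats the 8.1.1 symptom criteria as equivalent to the mild-or-worse definitions. The burden-of-disease score, VE against mild and against asymptomatic infection, and the symptomatic harm count depend on a boundary that the protocol draws in two ways.

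The stronger inference, that the trial's main efficacy result is at risk, is not supported. Moderate disease already requires new or worsening symptoms, so the primary endpoint is untouched, and VE against any infection combines both classes. Burden of disease is tested against a null of VE at or below 0, and even the most adverse illustration for symptomatic VE leaves 57.5%. The shift lowers VE against symptomatic disease, so it is conservative for that claim. The VE shifts should not be read as estimates, since all the inputs that drive them are assumed. The number of affected cases is not stated and is probably small.

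**What to change.** - In 8.1.3.2, require the listed symptom to be new or worsening relative to baseline, as 8.1.3.1 does, using the baseline SIC.
- In 8.1.3.4, define asymptomatic or undetected infection as a confirmed infection that meets none of the mild, moderate or severe/critical definitions. Leave the 24-hour and unexplained conditions in 8.1.1 as swab triggers only. A brief new symptom then counts as mild, and an unchanged chronic one does not.

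The cost is wording and one derivation rule. Section 8 already requires the baseline SIC before the first vaccination, and its severity ratings allow worsening to be derived. Slightly fewer mild cases will be counted. One limit remains: the baseline SIC covers only 24 hours, so an intermittent condition absent that day could still look new and would be left to adjudication.

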8.1.2. Procedures in the Event of (Suspected) COVID-19

8.1.2.1. Passive Follow-up (As of Amendment 7)

As of Amendment 7, active follow-up of suspected COVID-19 episodes will be replaced by a passive follow-up approach. For COVID-19 events that are ongoing at the time of informed consent:

[figure not shown]
- a. Participant will be instructed to stop using the eCOA.
- b. Any outstanding activities planned for the follow-up of COVID-19 events will end.
- c. No further sampling for participants and no Day 1-2, Day 3-5, and Day 29 visit will be performed.
- d. MRU and MA-COV forms are no longer to be completed.

The eCOA will be stopped based on approval of Amendment 7 at each study site. From that point onwards, active participants are no longer able to use eCOA.

For new suspected COVID-19 episodes no samples will be collected in the context of the study. Site staff will collect information on new COVID-19 episodes at scheduled time points and report these as SAEs, AEs, or MAAEs, as applicable. Participants may also contact the site at any time in between scheduled visits to report a safety concern (eg, hospitalization) or COVID-19 episodes. Concomitant medications for each COVID-19 episode are to be reported into the eCRF as well as any laboratory confirmation of COVID-19, if available. As of Protocol Amendment 7, there will be no further central testing for COVID-19 events.

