8. STUDY ASSESSMENTS AND PROCEDURES

Overview

The [Schedules of Activities](#) summarize the frequency and timing of all measurements applicable to this study.

Up to Amendment 7, all participants will be provided access to an eCOA digital tool. This eCOA will be used to collect COVID-19 signs and symptoms surveillance info for all participants, ePRO (Symptoms of infection with Coronavirus-19 [SIC], including body temperature, and pulse

oximetry results) for all participants at baseline and in case of COVID-19-like signs and symptoms, and e-Diary data on 7-day reactogenicity (solicited signs and symptoms, including body temperature) in the Safety Subset. All eCOA assessments should be conducted/completed before any tests, procedures, or other consultations to prevent influencing participant responses. Refer to the PRO completion guidelines for instructions on the administration of ePROs. The baseline SIC must be completed prior to the first vaccine administration.

As of Amendment 7, the number of on-site visits for participants who are not part of the Immunogenicity Subset is reduced. For these participants, any outstanding on-site visits will be replaced by phone call visits. No further booster vaccination will be provided in the protocol. In addition, requirements for COVID-19 episodes reporting are changed (ie, a passive follow-up approach is adopted, defined as safety follow-up phone call visits by the site instead of on-site study visits to document COVID-19 events as SAEs, AEs, or MAAEs until end of study). All participants will be reconsented at an unscheduled visit and as per local informed consent process guidelines.

If multiple assessments are scheduled for the same timepoint, it is recommended that procedures be performed in the following sequence: vital signs before blood draws. If needed, assessments may be performed on another day within the applicable visit window. Actual dates and times of assessments will be recorded in the source document, the eCRF, or the sample requisition form.

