- COVID-19 events ongoing at time of informed consent do not need to be reported as AEs, SAE, or MAAEs, only new onset of COVID-19 events need to be reported.

For participants in the Safety Subset (applicable to double-blind phase only):

- Solicited AEs, collected through an e-Diary, will be recorded for each vaccination from the time of vaccination until 7 days post-vaccination. If these solicited signs and symptoms are not resolved by that time, the participant will continue to complete the e-Diary until Day 29 post-vaccination or until they are resolved, whichever comes first.
- All other unsolicited AEs, whether serious or non-serious, will be recorded for each vaccination from the time of vaccination until 28 days post-vaccination. Unsolicited AEs with the onset date outside the timeframe defined above (>28 days after previous study vaccination), which are ongoing on the day of the subsequent vaccination, should be recorded as such.

After the unblinding visit, participants in the Safety Subset will stop the collection of solicited AEs and will not continue in the Safety Subset for any subsequent vaccination. Newly enrolled participants in the open-label phase will not participate in the Safety Subset.

Adverse Events of Special Interest

From the time of local approval of Protocol Amendment 5 onwards, TTS is considered to be an AESI. Suspected AESIs (thrombotic events and thrombocytopenia [defined as platelet count below 150,000/ μ L⁹]) will be recorded from the moment of vaccination until the end of the study/early withdrawal (see Section 8.3.7). An AESI Assessment Committee with appropriate expertise will be established to evaluate each suspected AESI and determine whether it is a case of TTS.

Serious Adverse Events

All SAEs, as well as PQCs, occurring during the study must be reported to the appropriate sponsor contact person by study-site personnel within 24 hours of their knowledge of the event.

SAEs, including those spontaneously reported to the investigator before the end of the study, must be reported using an SAE form. The sponsor will evaluate any safety information that is spontaneously reported by an investigator beyond the time frame specified in the protocol.

[figure not shown]
Up to Amendment 7, participants will be reminded once a month to contact the study site in case of an SAE. As from Amendment 7, this is replaced by the passive follow-up approach.

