9.7.4. Efficacy Analyses

For the analysis of efficacy in the open-label active phase, follow-up time will be expressed on a calendar time scale, and defined as time since a predefined calendar date, eg, study start or time period to start evaluation, to adjust for changing incidence over time.

The analysis will be conducted according to the regimen as received (see Section 3 for the main study cohorts).

Follow-up time (a participant at risk for an event) will begin on the date of administration of the first dose of the vaccine regimen under evaluation, expressed on a calendar time scale as time since

study start/predefined calendar date. Follow-up time and events occurring within 14 days since (last) vaccination may be ignored.

If deemed feasible, efficacy of the booster vaccination may be explored by comparing efficacy data after boosting to data in the absence of booster, on the same primary regimen. Feasibility will be assessed based on data availability as well as adjustments for potential confounding (including, but not limited to age, country and/or site, presence of co-morbidities). Additional factors may be added and prespecified in the SAP.

Efficacy data of the open-label active phase may be compared following a homologous vaccination schedule (Ad26 COV2.S) versus a heterologous vaccination schedule. The duration of protection of the booster vaccinations may be summarized (as early booster versus late booster vaccination).

All details will be described in the SAP.

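### Amendment 7 switches off the eCOA at site approval but exempts from reporting any COVID-19 episode ongoing at the participant's later consent, so episodes starting in between can escape both routes

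*Protocol*

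**What the plan says.** Protocol Section 8.1.2.1 replaces active follow-up of suspected COVID-19 with passive follow-up and sets the end of the eCOA by site: "The eCOA will be stopped based on approval of Amendment 7 at each study site". It adds: "From that point onwards, active participants are no longer able to use eCOA".

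The same section has a wind-down list introduced by "For COVID-19 events that are ongoing at the time of informed consent". Its first item is "Participant will be instructed to stop using the eCOA". Sampling for later episodes ends as well: "For new suspected COVID-19 episodes no samples will be collected in the context of the study". Central testing of COVID-19 events also stops under Amendment 7.

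Section 8 makes consent a separate step: "All participants will be reconsented at an unscheduled visit and as per local informed consent process guidelines".

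Section 8.3.1, in its list for all participants as of Amendment 7, states: "COVID-19 events ongoing at time of informed consent do not need to be reported as AEs, SAE, or MAAEs". It limits the reporting duty to events of new onset. Section 8.1.2.1 has site staff collect new episodes at scheduled time points and lets participants contact the site between visits.

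On analysis, Section 9.7 separates the active from the passive follow-up phase, and Section 9.7.4 says: "For the analysis of efficacy in the open-label active phase, follow-up time will be expressed on a calendar time scale". It states when follow-up time begins but not when it ends. The methods and the data to be included are left to the SAP.

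**The concern.** Two rules that should meet at one date are tied to two different dates. The exemption in Section 8.3.1 makes sense if every event ongoing at consent has already been picked up by active surveillance, because reporting it again would then duplicate it. That holds only while active surveillance runs up to consent. If the eCOA has already gone off at the site, the exemption also covers episodes that active surveillance never prompted.

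What is at stake is collection first and analysis second. A censoring rule in the SAP can correct a denominator, but it cannot recover an episode that nobody was required to record. In addition, if active-phase person-time ran on to consent, it would include time with weaker case detection, and the rates would tend to be too low.

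**Working it through.** The protocol gives no figure on this point to reproduce, so the rules are first applied to each type of episode.

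**Dates.** Let A be the day the eCOA goes off at a site (Section 8.1.2.1) and C the day a given participant consents under Amendment 7 (Section 8). Section 10.3.1 requires ethics committee approval of an amendment and its revised consent form before implementation, so C should not precede that approval. Participants at a site are unlikely all to be seen on one day, so C later than A is expected for many. No maximum interval appears in the sections available.

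**Episodes by onset.**

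| Onset | Status at C | Prompted by eCOA? | Passive reporting rule |
|---|---|---|---|
| Before A | Ongoing | Yes | Exempt, harmless because already captured |
| A to C | Ongoing | No | Exempt under 8.3.1 |
| A to C | Resolved | No | Unclear |
| After C | Not applicable | No | Reportable as new |

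The second row is the hole. The third is insecure for two reasons: no reference date is given for what counts as new, and site staff collect episodes at scheduled time points whereas reconsent is an unscheduled visit.

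**Serious events.** The exemption names SAEs. Elsewhere Section 8.3.1 requires all SAEs to be reported from first vaccination to the last study-related procedure, and Section 8.3.6 requires every event meeting the SAE definition to be reported as one. For a serious COVID-19 episode ongoing at C these provisions conflict.

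**Confirmation.** If the phrase as of Amendment 7 means site approval, then study sampling and central testing of new episodes also stop at A. Section 8.1.3 bases case analysis on central confirmation, so an episode telephoned in during the gap could not be confirmed that way.

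**Possible effect on rates, only if person-time ran to C.** Assume constant incidence. Let g be the gap in days, T the days counted as active phase including the gap, and s the share of gap cases still detected.

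Understatement = (g/T) × (1 − s)

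All inputs are assumptions: g from 14 to 90 days, T from 180 to 540 days. With s = 0:

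| T | g = 14 | g = 30 | g = 60 | g = 90 |
|---|---|---|---|---|
| 180 | 7.8% | 16.7% | 33.3% | 50.0% |
| 365 | 3.8% | 8.2% | 16.4% | 24.7% |
| 540 | 2.6% | 5.6% | 11.1% | 16.7% |

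With s = 0.5 each figure halves; for T = 365 and g = 30 it is 4.1%.

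For a comparison of cohorts with gaps gA and gB and s = 0, observed RR = true RR × (1 − gA/T)/(1 − gB/T). Equal gaps leave the ratio unchanged. With T = 365, gaps of 60 and 30 days turn a true ratio of 1.00 into 305/335 = 0.91; reversed, 335/305 = 1.10.

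**The case against.** A reader might infer three stronger things from these passages. The documents support none of them.

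*That Section 8.1.2.1 gives two rival end dates for active surveillance.* It does not. The consent clause heads a list for closing episodes already under way and sets no surveillance end for participants without an episode. For everyone else the eCOA stop is tied to approval. What remains is that the first item tells participants at consent to stop using a tool that may already be off, and that the exemption in Section 8.3.1 uses the consent date.

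*That no case can be detected in the gap.* Participants may inform the site directly (Sections 8.1.2.1 and 8.1.2.2), local confirmations are recorded, and the general SAE rules continue. The loss is of prompted detection and, on the site-approval reading, of central confirmation. The s = 0 figures are therefore upper bounds for their assumed gaps.

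*That active-phase rates are biased low.* Nothing available says that person-time runs to consent. Sections 9 and 9.7 leave this to the SAP, which is a normal place for it, and Section 3 may also bear on it. A request for a censoring rule alone would not be a fair criticism of the protocol.

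It is also fair to say that the gap is inferred, since no interval is stated and the wording on approval fixes no exact day. Section 9.7 makes the open-label summaries descriptive, and a shut-off set by site gives no stated reason for gaps to differ by cohort. These points limit the consequences. They do not close the second and third rows of the episode table, which arise from collection rules in the protocol itself.

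**Conclusion.** The point holds as a gap in case collection. An episode that starts after the eCOA goes off and is ongoing at reconsent falls outside prompted surveillance and is exempt from AE, SAE and MAAE reporting. One that starts and resolves in between has no clear reporting rule. For serious episodes the exemption also conflicts with the general SAE provisions in Sections 8.3.1 and 8.3.6.

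The number of episodes affected cannot be derived from the documents. The conclusion assumes that sites shut off the eCOA on approval, that some participants reconsent later, and that nothing in the Schedules of Activities, Section 3 or the SAP, which were not available for this check, aligns the two dates. Any understatement of active-phase rates is a conditional risk, and the percentages above are illustrations, not estimates. The double-blind primary analysis uses data only up to the unblinding visit (Section 9.4.1) and is untouched.

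**What to change.** Use one switch date per participant for both the end of eCOA surveillance and the reporting exemption. Either of these would do it:

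1. Keep the eCOA available until that participant's reconsent. The exemption in Section 8.3.1 then covers only events that active surveillance could have prompted.
2. Keep shut-off at site approval, and limit the exemption to episodes already under active follow-up on that date. At the reconsent contact, ask about every COVID-19 episode with onset since shut-off, resolved or ongoing, and record it as a passive-phase event.

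In either case, end active-phase person-time in the open-label SAP at the same date, and reconcile the SAE part of the exemption with the general SAE rules in Sections 8.3.1 and 8.3.6.

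The second option costs one question at the reconsent contact and a site memo. The first needs a memo and continued eCOA access for the length of the gap.
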